The maximum diameter of erosions will also be scored quantitatively:

Grade 1:  $>0$  but  $<2\text{mm}$

Grade 2:  $\geq 2$  but  $<3\text{mm}$

Grade 3:  $\geq 3\text{mm}$

Entheseal power Doppler will be scored on a semi-quantitative basis:

Grade 1: Mild changes

Grade 2: Moderate changes

Grade 3: Severe changes

The remainder of the assessments (hypoechoicity, enthesophytes, calcifications) will be scored present (1) or absent (0).

Once all aspects have been scored, the cumulative totals will be calculated to formulate and 'inflammation score' and a 'chronicity score'

Inflammation score: GS changes related to inflammation (enttheseal hypoechoicity and thickening) will be added to the PD scores.

Chronicity score: GS changes related to chronic findings (calcifications, erosions and enthesophytes) will be totalled.

US scores forming secondary endpoints will include 24 joints (bilateral wrists, MCPs 2&3, PIPs 2&3, knees, MTPs 1-5, ankle) and 10 entheses (bilateral quadriceps insertion, patellar ligament proximal insertion, patellar ligament distal insertion, Achilles tendon, plantar fascia). Exploratory analysis of synovitis and enthesitis will be performed in a subset of patients using scores calculated according to the newly published OMERACT definitions which include 48 joints (bilateral wrists, MCP1-5, PIP1-5, DIP2-5, knees, MTP1-5, tibiotalar, talonavicular and subtalar) and 12 entheses (bilateral lateral

epicondyle, quadriceps insertion, patellar ligament proximal insertion, patellar ligament distal insertion, Achilles tendon, plantar fascia) (42, 43).

Patients will be considered to be in US remission if the maximum score for any of the joints forming part of the established RA scoring protocol, and for any of the entheses scanned in all patients, is GS enthesal hypoechoogenicity score <2 and power Doppler score=0. On an exploratory basis this will be repeated using scores calculated in the joints and entheses included in the OMERACT definitions, in the subset of patients with these scores available.

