## APPENDIX 7: Tender and swollen joints assessments instructions

### Tender & Swollen Joint Assessment (count and grading)

Does the patient have any tender joints?

Yes  No

Does the patient have any swollen joints?

Yes  No

If YES, please indicate which joints are affected by grading (0-3) the relevant boxes.

		RIGHT		LEFT									
		TMJ											
		SCJ											
		ACJ											
		SHOULDER											
		ELBOW											
		WRIST											
		CMC											
		5	4	3	2	1	1						
		HAND MCPJ				2							
		HAND PIPJ				3							
		HAND DIPJ				4							
		5				5							
				NA		HIP		NA					
						KNEE							
						ANKLE							
						Tarsi							
		5	4	3	2	1	1	2	3	4	5		
		FEET MTPJ				2		3		4		5	
		FEET PIPJ				3		4		5			
		FEET DIPJ				4		5					
		5											
Total tender joints count (78 joints)						Total swollen joints count (76 joints)							
Total tender joints grading (78 joints)						Total swollen joints grading (76 joints)							
PsARC tender joints grading (68 joints)						PsARC swollen joints grading (66 joints)							

Please give details of any joints that are missing or not assessed:

Investigator Signature.....

Date.....

76/78 joints list encompasses all the joints depicted in the above mannequin (TMJ; SCJ/ACJ/Shoulder; Elbow; Wrist; CMC; MCPJ; hand PIPJ; hand DIPJ; HIP; Knee; Ankle (that is: tibio-tarsal joint); Tarsi; feet MTPJ; feet PIPJ; feet DIPfJ). 66/68 joints list encompasses all the above mentioned joint **with the exception of CMC and feet DIPJ**. HIPs are always excluded from the assessment of articular swelling.

Total grading for tender joints ranges 0-234; total grading for articular swelling ranges 0-228. The grading range of tender joints for PsARC calculation is 0-204 (CMC and feet DIPJ excluded). The grading range of articular swelling for PsARC calculation is 0-198 (CMC and feet DIPJ excluded).

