	8.6		Added clarification that the assessment of predictors/modifiers of treatment response will be made for response at 24 weeks	27/06/2023
	8.7		Typo in derivation of PASDAS corrected Typo in range of LDI corrected; description of calculation expanded to match development paper MDA criterion corrected to include BSA, to match development paper Joint and enthesal remission criteria corrected to match protocol Definitions of CPDAI 'not involved' category added; typos in criteria for scores of 2 & 3 corrected	20/06/2023 20/06/2023 20/06/2023 20/06/2023 20/06/2023
	9.2		Key exclusion criteria for derivation of per protocol population amended to include receipt of systemic steroids within 4 weeks prior to screening	20/06/2023
	11.3		References to exploratory subset analyses using 76/78 joints for the secondary outcomes MDA and ACR response removed, as the intention is to focus solely on PsARC response. Correction to planned correlation between joint counts and total US GLOESS, which will be assessed using screening values rather than baseline values, as US was performed at screening rather than baseline	27/06/2023
	12.4		Initial inspection of ALT results indicates skewed distributions, therefore the planned summaries have been amended accordingly, and details given as to the time-points at which the values will be summarised. References to changes from baseline have been removed in favour of summaries at each time-point.	
8.0	4.0	3.2.4	Unplanned endpoints i.e. PASDAS status and response variables, published since the inception of the trial, added in a separate section: 
• Very low disease activity (PASDAS<1.9)• PASDAS moderate or good response• PASDAS meaningful change value achieved (improvement >1.29)	09/11/2023 (post-unblinding)
	8.7		Unplanned PASDAS status and response variables, and sensitivity definitions of US remission, defined in the derived variable section	09/11/2023 (post-unblinding)

Protocol version	Updated SAP n ^o	Section changed	Description of and reason for change	Date changed
	11.4		New 'Additional unplanned analysis' section added to give details of analysis methods for unplanned endpoints and unplanned descriptive summaries	09/11/2023 (post-unblinding)

APPROVALS

Approved By:

Role: Chief Investigator

Name: [name]

Date: 17/11/2023

Signature: _____

Role: Sub-Investigator

Name: [name] [name]

Date: 17 – November - 2023

Signature: _____

Role: Trial statistician; SAP author

Name: [name]

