3.1.2 Secondary Objectives

Secondary objectives are:

- To assess superiority of combination therapy over standard care in improving ultrasound-detected joint and enthesal pathology
- To assess superiority of combination therapy over standard care in improving patient-reported quality of life and health status
- To assess whether responses on US imaging outcomes are associated with steroid therapy
- To assess the extent of association between clinical and US imaging joint assessments at baseline
- To assess the extent of association between clinical and US imaging responses to therapy
- To identify baseline variables which may be modifiers of clinical or imaging response (e.g. symptom duration, immunological parameters)
- To assess the test-retest reliability of the PASDAS composite index

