5. SEQUENCE OF PLANNED ANALYSES

5.1 *Interim Analyses*

There are no planned Interim Analyses for this study.

5.2 *Final Analyses and Reporting*

All final, planned, analyses identified in the protocol and in this SAP will be performed only after the last patient has completed the week 52 visit, with the exception of baseline analyses (see below). A blinded data review meeting will be held prior to database lock and completion of the final analyses.

In addition, no database may be locked, random code unblinded, or analyses completed until this SAP has been approved.

Key statistics and study results will be made available to the study team following database lock and prior to completion of the final CTR.

Analyses using either screening and baseline data (PASDAS test-retest reliability) or baseline data only (associations between clinical and imaging assessments at baseline) will be performed as soon as all the relevant patients have completed these visits and the relevant data have been fully validated and locked to further amendment. In the case of MRI, no analyses of the baseline data will be performed until all patients in the subset in whom MRI measurements were obtained at baseline have completed the follow-up MRI visits, and all MRI data have been fully validated, because MRI data from all visits will be scored simultaneously. As these analyses do not involve post-treatment efficacy comparisons and can be performed blind to treatment group there will be no impact on multiplicity and no potential to unblind the trial.

Any, post-hoc, exploratory analyses completed to support planned study analyses, which were not identified in this SAP, will be documented and reported in appendices to the CTR. Any results from these unplanned analyses will also be clearly identified in the text of the CTR.

Analysis of exploratory WB-MRI outcomes may be conducted after the primary and secondary outcomes have been analysed and reported; in which case this analysis will be attached as an addendum to the main CTR.

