US_TotalGS_Subset	US total grey scale scores across OMERACT list of joints	0-144	Total of GS scores (0-3) for 48 joints: bilateral wrists, MCP1-5, PIP1-5, DIP2-5, knees, MTP1-5, tibiotalar, talonavicular and subtalar
US_TotalPD	US total power Doppler scores across all common joints	0-72	Total of PD scores (0-3) for 24 joints: bilateral wrists, MCPs 2&3, PIPs 2&3, knees, MTPs 1-5, ankle
US_TotalPD_Subset	US total power Doppler scores across OMERACT list of joints	0-144	Total of PD scores (0-3) for 48 joints: bilateral wrists, MCP1-5, PIP1-5, DIP2-5, knees, MTP1-5, tibiotalar, talonavicular and subtalar
US_GLOESS	US total PDUS scores across all common joints	0-72	Total of PDUS scores (0-3) for 24 joints: bilateral wrists, MCPs 2&3, PIPs 2&3, knees, MTPs 1-5, ankle

Variable Name	Description	Valid Values (Ranges)	Computation Methods, Notes or Equations
US_GLOESS_Subset	US total PDUS scores across OMERACT list of joints	0-144	Total of PDUS scores (0-3) for 48 joints: bilateral wrists, MCP1-5, PIP1-5, DIP2-5, knees, MTP1-5, tibiotalar, talonavicular and subtalar
US_JointRemission	US number of common joints with GS>1 & PD>0 =0 (Y/N)	0-24	Count of joints with GS>1 or PD>0 in 24 joints: bilateral wrists, MCPs 2&3, PIPs 2&3, knees, MTPs 1-5, ankle = 0 (1 if yes, 0 if no)
US_JointRemission_Subset	US number of joints in OMERACT list with GS>1 & PD>0=0 (Y/N)	0-48	Count of joints with GS>1 or PD>0 in 48 joints: bilateral wrists, MCP1-5, PIP1-5, DIP2-5, 8 knee, MTP1-5, tibiotalar, talonavicular and subtalar = 0 (1 if yes, 0 if no)
US_NenthGS	US number of common entheses with GS abnormalities	0-10	Count of GS=1 for 10 entheses: Bilateral quadriceps insertion, patellar ligament proximal insertion, patellar ligament distal insertion, Achilles tendon, plantar fascia
US_NenthGS_Subset	US number of entheses in OMERACT list with GS abnormalities	0-12	Count of GS=1 for 12 entheses: Bilateral lateral epicondyle, quadriceps insertion, patellar ligament proximal insertion, patellar ligament distal insertion, Achilles tendon, plantar fascia
US_TotalEnthPD	US total power Doppler score across common entheses	0-30	Total of PD scores (0-3) for 10 entheses: Bilateral quadriceps insertion, patellar ligament proximal insertion, patellar ligament distal insertion, Achilles tendon, plantar fascia

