Pearsons product-moment correlation or Spearman's rank correlation, according to data type, will be used to quantify the extent of association between tender joint count, swollen joint count and total PDUS (US GLOESS) at screening. In specific joints for which both clinical examination and ultrasound scan were performed, sensitivity and specificity of tenderness, swelling and both tenderness and swelling for detecting joints scoring more than GS<2 and PD=0 will be calculated, together with associated 95% confidence intervals via the Wilson method.

To assess the extent of association between clinical and US imaging responses to therapy, an extended Cochran-Mantel-Haenszel test, stratified on poly/oligoarthritis and randomised treatment, will be performed on 24 week MDA versus 24 week US remission.

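### SAP 11.3 does not state the unit of analysis for joint-level sensitivity and specificity against ultrasound; if several joints per patient are pooled, the Wilson 95% intervals ignore clustering and are too narrow

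*SAP*

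**What the plan says.** One secondary objective is "To assess the extent of association between clinical and US imaging joint assessments at baseline" (SAP 3.1.2). Part of the analysis for it is in SAP 11.3: "In specific joints for which both clinical examination and ultrasound scan were performed", the sensitivity and specificity of tenderness, of swelling and of both together are to be estimated against ultrasound, and these "will be calculated, together with associated 95% confidence intervals via the Wilson method".

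A joint counts as ultrasound-positive if it fails the remission rule. SAP 8.7 applies that rule in the joint remission variable: "Count of joints with GS>1 or PD>0 in 24 joints". Protocol 8.3.1 lists the joints: "US scores forming secondary endpoints will include 24 joints (bilateral wrists, MCPs 2&3, PIPs 2&3, knees, MTPs 1-5, ankle". Those are 12 sites, left and right. All of them are also on the clinical list in Protocol Appendix 7 ("76/78 joints list encompasses all the joints depicted in the above mannequin"), so every patient can contribute up to 24 paired clinical and ultrasound readings.

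SAP 11.3 does not say whether a sensitivity is computed over all joints of all patients, over a joint group, for one site with both sides combined, or for one joint at a time. Protocol 11.5 does not mention the analysis.

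**The concern.** A Wilson interval assumes independent binary observations. Joints within one patient share the patient's pain threshold, disease pattern and, usually, the same examiner and ultrasonographer. Whether clinical examination agrees with ultrasound is therefore likely to be positively correlated across a patient's joints. If such joints are pooled, the effective sample size is smaller than the joint count and the interval overstates precision.

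Nothing else in the SAP covers this. The robust standard errors in 11.1 address heteroscedasticity in the primary regression. The mixed models in 11.2 are a fallback for repeated visits when multiple imputation fails. An analyst who pools and follows the text would report plain Wilson intervals.

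What is at stake is the stated precision with which clinical examination detects or misses ultrasound-positive joints, for part of one secondary objective.

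**Working it through.** The plan gives no joint count, precision target or design effect for this analysis, so there is no figure of its own to reproduce.

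**Inputs from the documents.** 84 patients (SAP 6). Joints per patient: 2 × (1 wrist + 2 MCP + 2 PIP + 1 knee + 5 MTP + 1 ankle) = 24. Pooled total: 84 × 24 = 2,016 joints.

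**Assumed inputs (not in the documents).** 25% of joints ultrasound-positive, sensitivity 0.40, specificity 0.90, within-patient ICC from 0.01 to 0.20 (0.30 for left/right pairs).

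**Step 1: Wilson intervals if all joints are pooled.**
- Sensitivity: 0.25 × 2,016 = 504 positive joints, 6 per patient. Wilson: 0.358-0.443.
- Specificity: 2,016 − 504 = 1,512 negative joints, 18 per patient. Wilson: 0.884-0.914.

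**Step 2: design effect with equal positivity, DE = 1 + (m − 1) × ICC**, where m is joints per patient. Approximate coverage of the unadjusted interval is 2Φ(1.96/√DE) − 1.

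| | m | ICC | DE | √DE | Approx. coverage |
|---|---|---|---|---|---|
| Sensitivity | 6 | 0.05 | 1.25 | 1.12 | 92% |
| Sensitivity | 6 | 0.20 | 2.00 | 1.41 | 83% |
| Specificity | 18 | 0.05 | 1.85 | 1.36 | 85% |
| Specificity | 18 | 0.20 | 4.40 | 2.10 | 65% |

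**Step 3: simulated coverage, 24 joints pooled** (beta-binomial, 12,000 replicates per setting). Each pair gives equal positivity across patients, then positivity varying between patients (ICC 0.2). At ICC 0 the Wilson interval covers 94.7% to 95.4%.

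| ICC | Sensitivity | Specificity |
|---|---|---|
| 0.01 | 94.6% / 93.8% | 92.9% / 93.0% |
| 0.02 | 93.7% / 93.0% | 90.8% / 90.3% |
| 0.05 | 91.5% / 89.2% | 84.6% / 84.7% |
| 0.10 | 87.7% / 84.2% | 76.2% / 75.5% |
| 0.20 | 81.6% / 75.6% | 64.6% / 63.2% |

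The equal-positivity values agree with Step 2. Specificity suffers more because each patient has more negative joints than positive ones.

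**Step 4: movement of the limits, varying positivity.**

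| | Wilson | Clustered, ICC 0.05 | Clustered, ICC 0.20 |
|---|---|---|---|
| Sensitivity | 0.358-0.443 | 0.350-0.452 | 0.331-0.473 |
| Specificity | 0.884-0.914 | 0.877-0.919 | 0.863-0.929 |

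The largest shift is 0.473 − 0.443 = 0.030. At ICC 0.05 none exceeds 0.452 − 0.443 = 0.009.

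**Step 5: smaller units.**
- MTPs 1-5 on both sides (10 joints), ICC 0.05 to 0.20: coverage 93.2% falling to 86.3% (sensitivity) and 91.0% falling to 79.5% (specificity).
- Left and right of one site, ICC 0.30: about 94% (sensitivity) and 92% (specificity).
- One joint per patient: about 95% at every ICC; Wilson is correct.

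**Step 6: other inputs.** With 20% positive, sensitivity 0.50 and specificity 0.80, pooled coverage is 90% and 84% at ICC 0.05, and 76% and 62% at ICC 0.20. The pattern does not depend on one choice of inputs.

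**The case against.** The strongest reply is that the plan may contain no error. The reference to specific joints in SAP 11.3 can be read as a joint-by-joint analysis, for which Wilson is right, and nothing in the section says joints will be pooled. The joint is clearly the object measured; only its aggregation is open. This stands, and it is why the conclusion is conditional. But the same phrase can equally mean the overlap of the clinical and ultrasound joint lists. A full site-by-site analysis would also give 12 sites × 3 clinical definitions × 2 measures = 72 estimates, and the SAP describes no such table. Both readings are open, and they lead to materially different stated precision.

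Second, every number on size rests on assumed inputs. That is true. The simulation also uses one ICC for all joint pairs and the same accuracy at every site. Letting accuracy differ between sites (assumed SDs of about 0.15 for sensitivity and 0.05 for specificity) raises coverage by roughly 1-2 points at ICC 0.05 and 2-4 points at ICC 0.20. That softens the shortfall but does not remove it.

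Third, the consequence is small: the limits move little, and no test, decision rule or between-arm comparison uses these intervals. This also stands, and it sets the priority.

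**Conclusion.** The concern holds in conditional form. The documents establish that the unit of analysis is unstated, that an independence-based interval is prescribed, and that no clustering provision applies. If several joints per patient are pooled and agreement with ultrasound is positively correlated within patients, the intervals are too narrow: negligibly at an ICC of 0.01, clearly at 0.05 and above, and more for specificity than for sensitivity. For left and right of one site the effect is small, and for one joint per patient there is none.

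The practical effect is modest. Point estimates, the patient-level correlations in the same section and the primary PASDAS analysis are unaffected. It is worth correcting because the remedy is cheap, but it is not a threat to the trial's conclusions.

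**What to change.** State the unit of analysis in SAP 11.3, including how left and right are handled. Then:

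- **Estimates pooled over several joints per patient** (all 24, or a group such as MTPs 1-5): keep the point estimate and replace Wilson with a patient-clustered 95% interval. This can be a logistic model or GEE with cluster-robust variance by patient, or a bootstrap that resamples patients. Under the assumptions above, the cluster-robust logistic interval covers 94.2% to 95.0% for pooled joints and was always estimable; the patient bootstrap at ICC 0.10 covers 93.3% to 94.8%.
- **One joint per patient, or left and right of one site:** keep Wilson. It loses at most about 3 points of coverage there. A clustered logit can fail when the observed proportion is 0% or 100%, which happened in 39% of replicates at 3% positivity and sensitivity 0.20 (left/right cells, ICC 0.20).

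The cost is one or two sentences and one Stata option, `vce(cluster id)`, for pooled estimates only; the reported intervals become wider. The v4.0 changes are dated "09/11/2023 (post-unblinding"), and SAP 5.2 lets baseline analyses run early, so in practice this means re-running the intervals, if joints were pooled, and reporting a documented deviation. The late change does not bias the trial result: as SAP 5.2 says of the baseline analyses, "As these analyses do not involve post-treatment efficacy comparisons and can be performed blind to treatment group".

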3.2 Study Endpoints

3.2.1 Primary Endpoint

The primary endpoint is clinical disease activity (PASDAS) at 24 weeks.

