3.2.2 Secondary Endpoint(s)

Secondary endpoints are:

Efficacy measures

Clinical measures of disease activity

- Disease activity measures:
 - PASDAS at 12, 36 and 52 weeks
 - Enthesitis score⁽²⁾ at 12, 24, 36 and 52 weeks
 - Dactylitis score^(3,4) at 12, 24, 36 and 52 weeks in patients with dactylitis
 - PASI score^[5] at 12, 24, 36 and 52 weeks
 - mNAPSI score^[6] at 12, 24, 36 and 52 weeks
 - CPDAI score^[7] at 24 and 52 weeks
- Acceptable state or response:
 - Proportion achieving MDA at 12, 24, 36 and 52 weeks
 - Proportion achieving PsARC response at 8, 12, 24, 36 and 52 weeks
 - Proportions achieving ACR20/50/70 responses at 12, 24, 36 and 52 weeks
 - Proportion achieving at least PASI75 at 12, 24, 36 and 52 weeks in the subset of patients in whom at least 3% of the BSA was affected by psoriasis at baseline
- Composite index test-retest reliability
 - PASDAS score at screening and at baseline visit

Imaging measures of disease activity

- Measures of joint/enthesis pathology
 - Total scores for synovitis/enthesis identified by US at 12, 24 and 36 weeks
 - GLOESS score^(8,9)
 - Inflammatory enthesitis score
 - Chronic enthesitis score
- Acceptable state
 - Proportion achieving US remission (all common joints and entheses (see section 8.7) score GS<2 & PD==0) at 12, 24 and 36 weeks

Patient-reported outcomes

- Patient VAS global disease activity at 24 and 52 weeks
- Quality of life
 - DLQI score^[10] at 24 and 52 weeks
- Health status
 - SF-36 mental component summary and physical component summary^[11] at 24 and 52 weeks.

Other secondary endpoints

- Treatment-related endpoints
 - Proportion of patients requiring additional steroid therapy up to week 12
 - Cumulative steroid dose received up to week 12*

*This was originally planned; however, inspection of blinded data indicates that all participants who received additional steroid received one IM dose of 120mg, therefore this analysis will not be performed as this is already captured in the proportion requiring additional steroid therapy

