US_EnthEro_Subset	US total erosion score across OMERACT list of entheses	0-36	Total of erosion scores (0-3) for 12 entheses: bilateral lateral epicondyle, quadriceps insertion, patellar ligament proximal insertion, patellar ligament distal insertion, Achilles tendon, plantar fascia
US_EnthInf	US total enthesis inflammation score across common entheses	0-70	=US_NenthGS+ US_TotalEnthPD +US_EnthThick
US_EnthInf_Subset	US total enthesis inflammation score across OMERACT list of entheses	0-84	=US_NenthGS_Subset+ US_TotalEnthPD_Subset+US_EnthThick_Subset
US_EnthChron	US total enthesis chronicity score across common entheses	0-50	=US_NenthCalc+US_EnthEro+US_NenthEnth

Variable Name	Description	Valid Values (Ranges)	Computation Methods, Notes or Equations
US_EnthChron	US total enthesis chronicity score across common entheses	0-60	=US_NenthCalc_Subset+US_EnthEro_Subset+US_NenthEnth_Subset
US_Remission	US remission in common joints	0 (No) to 1 (Yes)	=US_JointRemission==1 & US_EnthRemission==1 if US_JointRemission<. & US_EnthRemission<. (Equates to all common joints and entheses scoring GS<2 and PD==0)
US_Remission_Subset	US remission in OMERACT joint list	0 (No) to 1 (Yes)	=US_JointRemission_Subset==1 & US_EnthRemission_Subset==1 if US_JointRemission_Subset<. & US_EnthRemission_Subset<. (Equates to all scanned joints and entheses scoring GS<2 and PD==0)
US_JointRemissionSens	US remission in common joints (alternative definition)	0 (No) to 1 (Yes)	Count of joints with GS>2 or PD>0 in 24 joints: bilateral wrists, MCPs 2&3, PIPs 2&3, knees, MTPs 1-5, ankle = 0 (1 if yes, 0 if no)
US_EnthRemissionSens	US remission in common entheses (alternative definition)	0 (No) to 1 (Yes)	Count of entheses with GS>0 or PD>0 in 10 entheses: bilateral quadriceps insertion, patellar ligament proximal insertion, patellar ligament distal insertion, Achilles tendon, plantar fascia=0 (1 if yes, 0 if no).
US_ImagingRemissionSens1	US remission (alternative definition 1)	0 (No) to 1 (Yes)	=0 if US_EnthRemissionSens==0 or US_JointRemissionSens==0 =1 if US_EnthRemissionSens==1 & US_JointRemissionSens==1
US_ImagingRemissionSens2	US remission (alternative definition 2)	0 (No) to 1 (Yes)	=0 if US_EnthRemission==0 or US_JointRemissionSens==0 =1 if US_EnthRemission==1 & US_JointRemissionSens==1
US_ImagingRemissionSens3	US remission (alternative definition 3)	0 (No) to 1 (Yes)	=0 if US_EnthRemissionSens==0 or US_JointRemission==0 =1 if US_EnthRemissionSens==1 & US_JointRemission==1

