11.4 Additional unplanned analysis

After breaking the blind, we made the decision to additionally report PASDAS status and response variables that had been published since the inception of the trial. These were PASDAS very low disease activity, PASDAS moderate or good response, and PASDAS meaningful change value for improvement achieved (Y/N). These will be analysed according to the same methods indicated for the binary response variables i.e. adjusted estimates of effect size will be provided for binary secondary endpoints using multiple binary logistic regression; odds ratios and 95% confidence intervals will be presented. All analyses will control for the stratification factor and baseline values of the outcome where relevant. Two-sided significance at $p<0.05$ will be the criterion applied to indicate potential differences between treatment arms; however, as these comparisons were unplanned they will be considered exploratory.

In addition to these unplanned additional endpoints, unplanned additional descriptive summaries of total USGS and USPD will be presented, to help further illustrate that the lack of substantive change in US GLOESS (combined GS and PD score) was similarly observed for its sub-components.

Unplanned descriptive summaries of alternative definitions of US remission will be presented as the proportions achieving remission were very low, possibly because the criteria for joint remission were very strict.

Unplanned descriptive summaries of tender dactylitis count and 'any' dactylitis count will be presented to give further context to the LDI results, which only counts tender dactylitis.

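### The objective on the extent of association between clinical and ultrasound response is met only by a Cochran-Mantel-Haenszel test, with no effect estimate, on a remission outcome that few patients reached

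*SAP*

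**What the plan says.** SAP 3.1.2, matching Protocol 2.3, lists the objective: "To assess the extent of association between clinical and US imaging responses to therapy". The last paragraph of SAP 11.3 gives the method: "an extended Cochran-Mantel-Haenszel test, stratified on poly/oligoarthritis and randomised treatment", which "will be performed on 24 week MDA versus 24 week US remission". Protocol 11.5 adds no other method for this objective.

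US remission is defined in the derived-variables table of SAP 8.7 over 24 joints and 10 entheses: "Equates to all common joints and entheses scoring GS<2 and PD==0". SAP 11.4, written after unblinding, states that "the proportions achieving remission were very low, possibly because the criteria for joint remission were very strict". It adds descriptive summaries of alternative remission definitions but does not carry them into the association analysis.

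The objective on association before treatment is handled differently. In the preceding paragraph of SAP 11.3, Pearson or Spearman correlation "will be used to quantify the extent of association between tender joint count, swollen joint count and total PDUS (US GLOESS) at screening", and joint-level sensitivity and specificity are given with Wilson intervals.

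Continuous measures are also available on both sides at week 24. SAP 3.2.2 lists "Total scores for synovitis/enthesis identified by US at 12, 24 and 36 weeks", and SAP 3.2.1 says: "The primary endpoint is clinical disease activity (PASDAS) at 24 weeks".

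**The concern.** There are three parts.

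- **The output does not match the objective.** The objective asks how strong the association is. A CMH test addresses only whether it is zero, and the SAP names no measure of strength to go with it.
- **The test is weak if remission is rare.** A low overall number of US remitters is spread over four strata (arm by oligo/polyarthritis) and two MDA categories.
- **US remission is a state, not a response.** It has no baseline term, and entry (Protocol 6.3.1) sets no US activity threshold. A patient with little US pathology at screening could be counted as in remission without having changed.

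At stake is a stated secondary objective. A non-significant result could be taken to mean that clinical and US responses are unrelated when the test had limited ability to show a relation.

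**Working it through.** **Plan's own figures.** None is stated for this analysis. The trial size comes from the primary endpoint: 2 × (1.96 + 0.842)² × 1.57² / 1² = 38.7, so 39 per arm and 78 in total. With 5% drop-out, 39 / 0.95 = 41.05, so 42 per arm and 84 in total. Both match SAP section 6. About 84 × 0.95 = 80 patients would have week-24 data.

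**Assumptions.** The documents give neither the MDA nor the US remission proportion. I take 40% in MDA, four equal strata of 21, US remission of 3%, 5% or 10% (84 × 0.03 = 2.5, 84 × 0.05 = 4.2 or 84 × 0.10 = 8.4 patients), and a two-sided 5% level.

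**Test statistic.** For two binary variables the extended CMH test reduces to Q = [Σ(a − mt/n)]² / Σ[m(n − m)t(n − t) / (n²(n − 1))], compared with 3.84. In each stratum n is the number of patients, m the number in MDA, t the number in US remission and a the number in both.

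**Cell probabilities.** These are solved from the margins and the odds ratio. For 5% remission and an odds ratio of 5, remission is 9.44% in MDA and 2.04% outside it. Check: 0.4 × 0.0944 + 0.6 × 0.0204 = 0.050, and (0.0944/0.9056) / (0.0204/0.9796) = 5.0. Expected remitters are 84 × 0.4 × 0.0944 = 3.2 in MDA and 84 × 0.6 × 0.0204 = 1.0 outside it, over all four strata.

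**Simulated power** (repeat simulations differ by one or two percentage points):

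| US remission | Odds ratio 3 | Odds ratio 5 |
|---|---|---|
| 3% | 11% | 17% |
| 5% | 19% | 32% |
| 10% | 31% | 53% |

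At 3% the statistic cannot be computed in about 8% of simulated trials; at 10% it always can. With 20% remission (80 patients, 30% to 50% in MDA), power for these odds ratios would be 45% to 78%, so the rarity of remission drives the problem.

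**What an odds ratio would look like.** Take 80 patients, 32 in MDA, and 4 remitters: 3 of the 32 and 1 of the other 48. Ignoring strata, the crude odds ratio is (3 × 47) / (29 × 1) = 4.9. The conditional estimate is 4.8, with an exact 95% interval of 0.36 to 261. That interval shows how little is known, which a p-value alone would not.

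**Continuous alternative.** For a partial Spearman correlation with two covariates and n = 80, z = atanh(r) and SE = √(1.06 / (80 − 3 − 2)) = 0.119.

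- r = 0.3: z = 0.310, z/SE = 2.60, power Φ(2.60 − 1.96) = 74%; 95% interval about 0.08 to 0.49.
- r = 0.2: z = 0.203, z/SE = 1.71, power Φ(1.71 − 1.96) = 40%; 95% interval about −0.03 to 0.41.

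These values of r are illustrative; the documents give none.

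**Is MDA a response?** MDA needs 5 of 7 criteria, two of which are a tender and a swollen joint count of at most 1. Entry requires at least 2 tender and 2 swollen joints, so almost every patient fails both at the start and could be in MDA only by meeting all five others. The match is not exact, because entry uses the 78/76 joint set and MDA the 68/66 set. Even so, week-24 MDA largely reflects improvement. No such argument applies to US remission.

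**The case against.** Several points against the concern have force.

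- **No remission count is given.** A reader might infer that the remission column is nearly empty and the test almost hopeless. The SAP says only that the proportions were very low. At 10% remission and an odds ratio of 5, power is about 53%. That is weak, but not negligible.
- **An odds ratio is not excluded.** SAP 11.2 presents odds ratios with intervals for binary secondary endpoints, and one could be taken from these tables. The gap is an omission rather than a decision to report only a p-value. It remains a gap, since no estimate is planned for this objective.
- **Both variables might be dismissed as non-responses.** That goes too far for MDA, which the SAP lists under acceptable state or response and which mostly marks improvement here. The criticism holds for US remission in principle. If few patients were in remission at week 24, however, few can have been there from the start.
- **Correlating changes has its own weakness.** SAP 11.4 also reports that GLOESS and its grey-scale and Doppler components did not change materially. If individual changes are small as well, measurement error may weaken any correlation. The documents give no variance of change, so this is a risk rather than a finding.
- **Timing.** The low remission rate is documented only in SAP 4.0, after unblinding. A reader might conclude that the correlation should become the main analysis. Replacing a pre-specified test once results are known is not defensible; adding a labelled exploratory analysis is, and SAP 11.4 already does this for other endpoints.

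**Conclusion.** The concern holds in limited form. The planned analysis does not deliver the extent of association that the objective asks for, because no effect estimate or interval is specified. Under the assumptions above, power for an odds ratio of 3 is about 11% to 31% as US remission runs from 3% to 10%, and for an odds ratio of 5 about 17% to 53%. A non-significant result would not be evidence that clinical and US responses are unrelated.

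The size rests on assumed MDA and remission proportions and on equal strata; the lack of an estimate rests on the SAP text alone. The documents do not support calling the test incapable of showing an association, or treating MDA as unrelated to change. The primary analysis, sample size, treatment comparisons and safety analyses are untouched.

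**What to change.** In SAP 11.3:

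1. Keep the pre-specified CMH test. Report with it the MDA by US remission cell counts in each stratum and the Mantel-Haenszel odds ratio with an exact 95% confidence interval.
2. Add partial Spearman correlations with 95% confidence intervals, adjusted for arm and oligo/polyarthritis, for change from pre-treatment to week 24: US_GLOESS with PASDAS, with swollen joint count and with tender joint count; and US_EnthInf with LEI.
3. Label item 2 as specified after unblinding and exploratory, placed alongside SAP 11.4. State that it will be interpreted through the intervals, because limited change in GLOESS may attenuate the correlations.
4. State that a non-significant CMH result will not be read as absence of association.

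The cost is SAP wording, one odds ratio and four exploratory correlations, all from data already collected. The downside is several more estimates that must be marked post hoc.
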